9.6. Data Management

N/A.

9.7. Data Analysis

All variables will be analyzed descriptively. Cohorts will be compared; however, the main analysis will be between apixaban vs warfarin. Other comparisons (DOAC vs warfarin and DOAC vs DOAC) will be optional depending on the sample size. Means, medians, and standard deviations will be provided for continuous variables when performing descriptive analysis of continuous data. Numbers and percentages will be provided for dichotomous and polychotomous variables when performing descriptive analysis of categorical data. Bivariate comparisons of baseline characteristics and outcomes measures will be provided. Appropriate tests (eg, t-test, chi-square test) will be used based on the distribution of the measure. The incidence rate of stroke/SE, MB, and net clinical benefit will be calculated. The incidence rate will be calculated as the number of patients who experience the event divided by the observed time at risk. Kaplan-Meier survival curves will be generated to illustrate time-to-first stroke/SE, MB, and net clinical benefit. Statistical tests of significance will be conducted to determine differences between the cohorts. Baseline and outcome tables will be stratified by obese, severely obese, and index dose of DOAC.

All data analysis will be executed using statistical software SAS version 9.4 (Cary, NC).

9.7.1. Analysis Plan for Primary Objective

Baseline demographic and clinical factors such as age, sex, geographic region, baseline medications, and co-morbidities among NVAf patients initiating OAC will be summarized. Descriptive statistics, (ie, mean, standard deviation, median, and inter-quartile range for continuous variables and differences across treatments) will be compared using the Student's t-test or Wilcoxon rank sum test. Percentages for categorical and binary variables will be presented for all baseline patient characteristics and will be compared using the chi-square test or Fisher's Exact test.

The cumulative incidence rate for clinical outcomes (stroke/SE, MB, net clinical benefit) will be calculated. MB will be stratified by GI bleeding, ICH, and other bleeding; Stroke/SE will be stratified by hemorrhagic, ischemic, and systemic embolism. The incidence rate will be calculated as the number of patients who experience the event divided by the observed time at risk. The incidence rate will be calculated per 100 person-years.

Inverse Probability Treatment Weighting (IPTW)

Inverse probability treatment weighting (IPTW) will be used to balance patient characteristics when comparing outcomes among different cohorts. Three sets of IPTW will be conducted (all patients, obese patients, and severely obese patients). Depending on sample size, IPTW will also be conducted for the standard dose patients separately. In addition, the primary analysis will be conducted for apixaban vs warfarin and depending on the sample size, other OAC comparisons will be conducted.

IPTW uses propensity scores to obtain estimates of the average treatment effect. The propensity score will be calculated using a logistic model with treatment cohorts included in the model, using warfarin patients as the reference (ie, control cohort). The propensity score is defined as the probability of a patient receiving a certain treatment or not conditional on their observed baseline covariates (eg, age, gender, comorbidities, medications, etc.). The list of variables included in the logistic model will be based on clinical rationale. The propensity score acts as a balancing score between the cohorts. After calculating the propensity score, the distribution of the propensity scores will be reviewed. Each patient will be weighted by the inverse of the probability of their treatment option (weight=1/propensity score).

If a treated patient has a very low propensity score, a very large weight will be generated. Large weights can increase the variability of estimated treatment effect. In order to address this, the weights will be stabilized. In order to stabilize the weights, the treatment option and control weights will be multiplied by a constant, equal to the expected value of being in the treatment or comparison cohorts, respectively (see below). This reduces the variability of the weights and reduces the variance of the treatment effect estimates.

$$\frac{\sum_{i=1}^{N_T} PS_i}{N_T} * \frac{1}{PS_i}$$

The distribution of the stabilized weight will be reviewed. If no extreme outliers are observed, the stabilized weights will be applied to the sample. In cases of extreme outliers, the large weights could be set to a less extreme value (eg, recoding all weights that are outside 5th and 95th percentile to the 5th and 95th value, respectively). If needed, truncation can be done after stabilizing the weights.

After the weights are applied, the balance of the baseline covariates will be assessed. First, the means and proportions of baseline variables will be compared. The standardized difference compares the difference in means in units of the standard deviation. If the standardized difference is less than 10%, the covariates will be considered balanced. For continuous variables, the balance of the distribution will also be assessed. The high-order moments and interactions between variables should be similar between cohorts. The standardized difference will be used to compare the mean of the square of continuous variables. Graphical comparisons of the distribution of continuous variables will be completed. Side-by-side boxplots and empirical cumulative distribution functions will be used to compare the distribution of continuous covariates in the unweighted and weighted samples. Since the graphical approach can be subjective, a numerical method for comparing the distribution of continuous baseline covariates will also be completed.

Kolmogorov-Smirnov test allows a comparison of the distribution of a continuous variable between two independent groups.³³⁻³⁶

Cox Proportional Hazards Model

Cox models will be used to compare the risk of stroke/SE, MB, and net clinical benefit between cohorts. Variables that are not balanced in the weighted population will be included in the models in addition to treatment variables. For the secondary objective, an interaction term for treatment and obesity status will be included in the models. The proportional hazards assumption will be evaluated by visually inspecting the Kaplan-Meier plot. If the proportional hazards assumption appears to be violated, it will be confirmed by testing the significance of interactions between treatment and log of time.

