8.1.1. Primary Objectives

Aim 1: Evaluate the demographics and clinical characteristics of obese and severely obese NVAf patients initiating OACs (all patients, standard dose, and low dose; primary analysis will compare apixaban vs warfarin).

Aim 2: Determine if there is a difference in OAC treatment effect between obese and non-obese and severely obese and non-severely obese patients for stroke/SE, MB, and net clinical benefit.

Aim 3: Compare the risk of stroke/SE, MB, net clinical benefit among obese and severely obese NVAF patients initiating OACs (primary analysis will compare apixaban vs warfarin).

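### Primary Aim 2's treatment-by-obesity interaction would rest on pooled IPTW weights, with no weights for the comparator groups and no balance rule inside obesity groups

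*Combined protocol and SAP*

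**What the plan says.** Section 8.1.1 lists Aim 2 as primary: "Determine if there is a difference in OAC treatment effect between obese and non-obese and severely obese and non-severely obese patients".

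Section 9.7.1 then sets out the method:

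- **Weight sets:** "Three sets of IPTW will be conducted (all patients, obese patients, and severely obese patients". No set is listed for non-obese or non-severely obese patients.
- **Propensity model:** "The list of variables included in the logistic model will be based on clinical rationale". Obesity-by-covariate terms are neither required nor excluded.
- **Balance rule:** "If the standardized difference is less than 10%, the covariates will be considered balanced". The comparison is between treatment cohorts after weighting.
- **Higher-order balance:** "The high-order moments and interactions between variables should be similar between cohorts". The operational sentence that follows is "The standardized difference will be used to compare the mean of the square of continuous variables".
- **Fallback:** covariates found unbalanced in the weighted population are added to the Cox model.
- **Interaction:** "For the secondary objective, an interaction term for treatment and obesity status will be included in the models". No weight set is named.

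Section 9.7 adds "Baseline and outcome tables will be stratified by obese, severely obese, and index dose of DOAC". It does not name the two comparator groups or say whether these tables are weighted.

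**The concern.** The interaction is a ratio of two hazard ratios, each estimated inside one obesity group. It is unconfounded only if apixaban and warfarin patients are comparable inside each group. Weights from one propensity model without obesity-by-covariate terms balance a covariate on average over the groups. They do not force balance in either group. If older or sicker patients are steered towards one drug more strongly in obese than in non-obese patients, the residual imbalances have opposite signs and cancel in the overall standardized difference. The Cox fallback is then not triggered, because it responds to imbalance in the weighted population as a whole. A difference in treatment effect could be reported for a primary aim, or a real one masked, without any specified step signalling trouble.

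Two inconsistencies bear on the same analysis. Section 9.7.1 ties the interaction to the secondary objective, whereas Aim 2 is primary and the readable secondary aim (Aim 4) concerns warfarin patients only. In addition, the first inclusion criterion in section 9.2.1 admits only obese or severely obese patients. Read literally, that leaves no non-obese comparator.

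**Working it through.** **The plan's own figure.** Section 9.5 gives no calculation for the interaction. Its main-effect figure is 7,945 per cohort (HR 0.63, warfarin rate 1.10 per 100 person-years, power 80%, alpha 0.05).

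- Schoenfeld events, two-sided: 4 × (1.960 + 0.842)² / (ln 0.63)² = 147.1.
- Event probability under uniform accrual over 4.5 years, with loss of 55% (warfarin) and 40% (apixaban) read as annual: 0.00996 and 0.00820.
- 147.1 / (0.00996 + 0.00820) ≈ 8,101 per cohort, 2.0% above the stated 7,945.

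This neither supports nor weakens the point. It shows that the follow-up model used in the last step below is close to the plan's.

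**Size of the bias.** Assumptions, none supplied by the documents: one standard normal confounder with HR 1.6 per SD; no true drug effect; pooled logistic propensity model with main effects for obesity and the confounder; obese share 50%, or severely obese share 12%. The apixaban share is 20,000/56,000, from section 9.5.

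Let Δ be the difference between the two groups in the log-odds slope of apixaban on the confounder. After pooled weighting, the within-group standardized differences (SMDs) lie about Δ SD apart, so

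spurious ratio of HRs ≈ exp(−Δ × ln 1.6), with ln 1.6 = 0.470.

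- Δ = 0.3: exp(−0.141) = 0.87
- Δ = 0.2: exp(−0.094) = 0.91
- Δ = 0.1: exp(−0.047) = 0.95
- Δ = 0: 1.00

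Full calculation with stabilized weights (the heavier group is the obese or severely obese group):

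| Slope, lighter / heavier group | Heavier share | Overall SMD | SMD lighter | SMD heavier | Ratio of HRs |
|---|---|---|---|---|---|
| 0 / −0.3 | 50% | 0.1% | +15% | −15% | 0.87 |
| 0 / −0.3 | 12% | 0.0% | +4% | −26% | 0.87 |
| +0.1 / −0.1 | 50% | 0.0% | +10% | −10% | 0.91 |
| 0 / −0.1 | 50% | 0.0% | +5% | −5% | 0.95 |
| −0.2 / −0.2 | 50% | 0.0% | 0% | 0% | 1.00 |

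In the first row the group HRs are 1.07 and 0.93, and 0.93/1.07 = 0.87. Adding the obesity-by-confounder term to the propensity model gives a ratio of 1.00 in every row.

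A second calculation used a binary confounder (prevalence 30%, HR 2 to 3) and a true HR of 0.63 in both groups. With confounder-treatment odds ratios of 1.25 and 0.80 in the two groups, the overall difference is 0.0% and the ratio 0.89 to 0.93. With equal odds ratios the ratio is 1.00.

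**Would the interaction sentence catch it?** Suppose the 10% rule is applied to the weighted obesity-by-confounder product. In the first row it is about −10.7% and fails. In the second it is about −9% and passes, although the severely obese group is at −26%. In the third it is about −7% and passes.

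**Against random error.** Assume 20,000 apixaban patients, 20,000 to 36,000 warfarin patients and 50 to 60% obese. Expected strokes are about 163 on apixaban and 199 to 358 on warfarin. The SE of the log ratio is the square root of the summed reciprocal cell counts; at 50% obese and 20,000 warfarin patients, √(2/81.5 + 2/99.5) = 0.21. The range is 0.19 to 0.22. A ratio of 0.87 (log −0.139) is then 0.63 to 0.73 SE from the null. At the 0.10 interaction cutoff in the section 9.8 checklist, the false-positive chance is about 17 to 19%. At 0.91 it is 13 to 14%, against a nominal 10%.

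**The case against.** Several counterarguments have force.

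- **The all-patients set is not the only candidate for the severe contrast.** Under section 9.2.3 the obese set also holds both severely obese patients and non-severely obese patients with BMI 30 to 40. A reader might infer that Aim 2 can run only on the all-patients weights. That holds for obese versus non-obese, not for the severe contrast. Pooled weights within the obese set would raise the same issue.
- **The plan does mention interactions.** A reader might infer that within-group balance is ignored and that the plan's check would always pass. BMI and weight are baseline variables, so the sentence on interactions can be read to cover obesity-by-covariate products, and at 10% it would flag the first scenario above. It does not name obesity and has no measure or threshold. It would miss the other two scenarios.
- **The bias is conditional.** A reader might infer that any reported effect difference would be pure confounding. The documents do not support that: no figure shows that drug choice depends on covariates differently by obesity group, and clinical rationale could lead to the needed terms being included. With equal slopes there is no bias.
- **A within-group 10% check is not sufficient either.** In the third scenario the group differences sit at about 10% and the ratio is still 0.91. This stands.
- **Redaction.** Parts of section 9.7.2 and of the secondary objectives are blacked out, and section 9.7.1 assigns the interaction to the secondary objective. Further detail may sit there.

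The separate balance checks for the obese and severely obese sets do not answer the point. They concern different weights and include no comparator group.

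**Conclusion.** The concern holds as a gap in specification with a cheap and better alternative, not as a demonstrated bias. As readable, primary Aim 2 would use pooled weights, with no obesity-by-covariate terms specified and no balance rule inside obesity groups. The overall 10% check can then pass while the interaction is biased. Under assumed slope differences of 0.2 to 0.3 and a confounder HR of 1.6 per SD, the spurious ratio is about 0.87 to 0.91. That is less than one standard error of the log ratio for the obesity contrast, so it would distort the answer to Aim 2 rather than dominate it. The plan should be amended before the interaction is analysed. Confidence is moderate: the slopes and confounder strength are assumptions, and redacted text may say more.

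**What to change.** 1. For Aim 2, fit the propensity score separately in obese and in non-obese patients, and separately in severely and in non-severely obese patients. A single model with obesity-by-covariate terms is an acceptable alternative. Stabilize the weights within each group.
2. Fit the Cox model with treatment, obesity status and their product on these weights. The obese and severely obese patients then carry the same weights in Aims 2 and 3.
3. Report apixaban-warfarin standardized differences inside each group against the 10% rule. This supplements step 1 and does not replace it, since about 10% inside groups can still give a ratio near 0.91.
4. In the Cox paragraph of section 9.7.1, replace the reference to the secondary objective with Aim 2 (primary).
5. Reconcile the first inclusion criterion in section 9.2.1 with the non-obese comparator that Aim 2 and section 9.2.3 require.

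The cost is revised wording, two further propensity models with their balance tables, and slightly more variable weights in the small severely obese group. No new data are needed.

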9.7.2. Analysis Plan for Secondary CCI [REDACTED]

Any further comparisons or sub-group analysis will be assessed and conducted based on feasibility analysis to ensure adequate sample size through power calculation.

CCI [REDACTED]

[REDACTED]

[REDACTED]

CCI [REDACTED]

[REDACTED]

Sensitivity Analysis: Propensity Score Matching

The propensity score matching (PSM) technique will be used to control for potential confounders when comparing the cohorts.³⁷ Covariates to be included in the logistic regression model may include the following variables: age, geographic region, Charlson comorbidity index score, comorbidities, and other clinical characteristics. The final list of

variables to be used in the model will be discussed and determined during analysis development, after reviewing the pre-matched descriptive tables. Each subject in the reference cohort will be matched to a subject in the comparator cohort with the closest propensity score. The nearest neighbor method without replacement and with a caliper of 0.01 will be used to select the matched samples. The balance of covariates between treatment groups will be determined using the absolute standardized difference of the mean ≤ 0.10 .

After PSM, no significant differences are expected among all pre-index measures between the patient cohorts. PSM with a different ratio (1:2 or 1:3) can also be considered if the matched sample size using a ratio of 1:1 is too small.

9.8. Quality Control

STATinMED Research's approach combines scientific rigor with accurate results. The company focuses on quality at each step of the process, including, but not limited to the following:

- Sound scientific design and clinically rigorous review.
- Detailed study protocol, that includes definitions, codes, analyses, and table shells. A member of the STATinMED clinical team will review the appropriateness and validity of the coding strategy and identify relevant issues. The protocol further provides STATinMED Research and Pfizer the opportunity to solidify research questions and to address any potential gaps in information.
- Rigorous quality assurance checks will be performed during the construction of the dataset. Several checks are used, including record-level verification of all data elements, double programming of certain portions of the dataset, programming data edit checks, visual review of raw data against the constructed data elements, and review of analysis to assess validity of results.
- STATinMED Research's analysis will be performed by an analyst under the supervision of the project manager, lead analyst, and/or vice president. These team members review programs and output for consistency with the analysis plan, quality, and accuracy. Further, results will be reviewed with Pfizer to establish that the results meet Pfizer's expectations.

Additional quality control procedures are enlisted below.

QC Checklist	Initials
QC of Excel File	

 Evaluate each step of attrition table (eg, check percentage drop at each step, compare to prior studies (rerun, other internal, external (if applicable))). 	

 5 separate database equal total pooled population (pre-match and post-match). 	

 Check percentage drop after PSM (expect ~10% drop but dependent on database/original sample size; add PSM sample size to attrition table). 	

 Baseline table → ensure all categorical variables equal 100% and total sample size, make sure all three dose variables are complete (Auto-check using formulas). 	

 Outcome table → components of MB or stroke/SE should be equal or larger than overall MB or stroke/SE (N and incidence rates; auto check using formula), all other categorical variables equal 100% and total sample size, minimum follow-up should be at least 1 day and check distribution. 	

 Outcome table → ensure incidence rates can be calculated using number of events and person time 	

 Check conditional formatting for p-values and standardized difference (red for p-values <0.05 (unless interaction p-value where the cutoff is <0.10), green for standardized difference ≥10.00). 	

 (Rerun) Compare percent difference between original and new results (10% cutoff) in baseline and outcome tables (using formula). 	

 Compare incidence rates, KM curves, and Cox model results to ensure alignment (eg, compare log rank test to Cox model, visually inspect KM curve, can calculate IRR to see similarity to HR). 	

 Ensure pooled dose pre-match table has the same sample size as indicated in baseline table. 	

 Sample size in subgroup matches the sample size in baseline table (eg, CHF subgroup tables match CHF baseline row in pooled baseline table). For each analysis, will be customized for the subgroups. 	

 Sample size of combined subgroup equals total population (for interaction). 	

 If lower CI is >1 or upper CI is <1, then p-value should be <0.05 (using formula). 	

 Check duplicates within a sheet for Cox models (using formula). 	

Data Integrity Review Tasks for Publications (will be customized for each manuscript; each figure and table will be listed) – Completion by medical writer and data check against excel file by non-project team member
	

Check whether all data sources are annotated and traceable for future retrieval.
	

Check the following data by comparing it against the appropriate source documentation (including, but not limited to):
	

QC Checklist	Initials
QC of Excel File	

 Numbers, units, and symbols (for example, >, <, ≥, *) in text. 	

 Numbers, units, and symbols in all tables. 	

 Numbers and units (including those on axes) and symbols in all figures, including flow charts and diagrams. 	

 Measurement units. 	

 Data-driven statements. 	
Check that all data values are consistent throughout the document sections, tables, figures, legends, and footnotes (for example, data in the abstract match data in the body of document, and results section match figure).	
Check that values from other sources match reference.	
For any items not completed and marked N/A, provide rationale below.	
Additional comments.	
Click here to enter text.	

9.9. Limitations of the Research Methods

A key strength of this study design is that retrospective observational analyses provide a better understanding about the study population in real-world clinical practice and offer complimentary information to controlled clinical trials. Retrospective observational studies also allow the evaluation of patients who are often under-represented in clinical trials, such as those with comorbidities and older adults. Since prescribing patterns in the real world can be complex, retrospective analysis provides a more comprehensive picture of how medications are used by clinicians in routine practice. In addition, the claims databases include all medical and pharmacy claims of patients and allow for longitudinal analysis of a nationally representative sample.

A second key strength of this study design is the linked VA and Medicare databases, which allow us to see a comprehensive patient journey and health resource utilization across two databases. The VHA database includes lab values that will be used to identify obese and severely obese patients as opposed to ICD codes only. Additionally, INR values are available in the VHA data, which will also be evaluated to provide insights into warfarin management.

While claims data are extremely valuable for the efficient and effective examination of health care outcomes, treatment patterns, HCRU, and costs, all claims databases have certain inherent limitations because the claims are collected for administrative purposes and not research. For instance, the presence of a claim for a filled prescription does not indicate that the medication was taken as prescribed or at all. Medications filled over the counter or provided as samples by the physician cannot be observed in the claims data. And the presence of a diagnosis code on a medical claim does not indicate the positive presence of

disease, as the diagnosis code may be incorrectly coded or included as rule-out criteria rather than actual disease.

